## **Methods:**

### **Study Design:**

Single-arm study involving five (5) subjects undergoing 6 90-minute sessions of Pulsed Electromagnetic Therapy. All patients received the same treatment. Harnesses were placed on the head, wrists, and ankles of the body to conduct the electromagnetic frequencies. Patients were encouraged to rest and relax whilst the therapy was conducted, as it does not require any tasks by the patient. Patients were required to complete a questionnaire before and after the trial. This questionnaire enquired about the different symptoms related to PTSD and Trauma, and asked patients to rate their symptoms on a scale. These questionnaires would form the foundation of the study's findings, as it would give a clear comparison of symptoms before and after the trial.

All aspects of the trial were exempt from a U.K. ethics committee board review because the trial was a non-invasive method of treatment, did not collect and tissue or fluid samples and the device is CE-marked and had been used in other trials previously approved and published on Clinical Trials.gov. Documents were provided on clinicaltrials.gov as evidence of this exemption.

All patients were from the inclusion criteria, and any patients exhibiting cases from our exclusion list were rejected from the pilot study. Patients were recruited through the National Centre for Electromagnetic Therapy social media pages, including Facebook, Instagram, and [www.ncet.co.uk](http://www.ncet.co.uk).

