## Results & Findings

### **Prior to the Trial**

Once participants had been screened and approved for clinical trial study, they were required to fill out a questionnaire that sought to establish the specific issues that they were experiencing due to PTSD and Trauma. These responses were weighted as an average and are provided below.

For clarification, a rating of one (1) on the scale indicates a very severe case of a specific symptom, five (5) means a frequent feeling of a symptom, and ten (10) indicates that the symptom is not experienced at all. A weighted average score has been chosen as a foundation for our results, to compare them more accurately before and after the trial. However, specific notes and observations shall be included where needed.

Statements were also used, whereupon a patient would respond with either Daily (3 or more times a week), Weekly (2 to 3 times a week), Monthly (3 to 4 times a month), or Rarely (Once every 3 months or longer).

Question	Average Score
Have you experienced or witnessed a life-changing event that caused intense fear, hopelessness or horror?	All patients recorded 'Yes'.
Have you experienced either repeating dreams, flashbacks, or intense physical/emotional stress that relate back to the	Daily – 1 Patient Monthly – 2 Patients Rarely – 2 Patients

traumatic event(s)?	
Do you avoid thoughts, feelings, actions, conversations, or people related to the event?	Daily – 1 Patient Weekly – 2 Patients Monthly – 1 Patient Rarely – 1 Patient
Have you felt detached or negative towards yourself or others since the traumatic event(s) happened?	Daily – 4 Patients Monthly – 1 Patient
Do you have problems sleeping?	Daily – 1 Patient Weekly – 2 Patients Rarely – 2 Patients
Do you become increasingly irritable, angry, or engage in self-destructive behaviour?	Daily – 1 Patient Monthly – 3 Patients Rarely – 1 Patient
How long have your symptoms persisted?	Longer Than Three Years – 3 Patients Longer Than A Year – 1 Patient 8-12 Months – 1 Patient
Do you experience heightened version of anxiety, sensitivity, or depression?	Daily – 3 Patients Weekly – 1 Patient Monthly – 1 Patient
Rate Your Quality of Life	Average Score: 6
Rate The Severity of Depression	Average Score: 6.4
Rate How Difficult It Is To Fall Asleep	Average Score: 5.6
Rate The Severity of Flashbacks Relating to a Traumatic Event	Average Score: 5
Rate The Severity of Headaches or 'Brain Fog'	Average Score: 4.6
Rate The Severity of Fatigue	Average Score: 5

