## Discussion

Regarding nearly all the symptoms analysed in the clinical trial, there was a mild to significant improvement. The largest improvement of an average of 2.6 points was discovered in symptoms related to insomnia and anger outbursts. It can be hypothesised that due to increased rest and relaxation, patients were able to manage their negative emotions more efficiently.

Positive results were also found within the patients' own value of life. Large improvements were found in a patients' perception of overall happiness, satisfaction and fulfilment, as well as general quality of life. All these values increased by a score of 2 or more on average. It is evident that the PEMF treatment is beneficial in providing patients with a relaxing and calm therapy which in turn helps appreciation for quality of life, and motivation in facing daily tasks head on.

Physical symptoms were also improved using PEMF therapy. Issues relating to headaches, fatigue, and flashbacks were all reduced over the course of the trial. Patients reported feeling more relaxed, and physical pains has subsided (See 'Patient Four' below).

It is important to note that the only symptom that experienced no average change was depression. It can be postulated that this is due to depression being a more deep-rooted issue which was prevalent for an extended period prior to the clinical trial. It is promising to see that cases of depression were not worsened during the trial, indicating that PEMF therapy is able to improve symptoms related to depression (fatigue, insomnia, anger). Nonetheless, the lack of change in depression forms a consideration for future clinical trials (see 'Considerations').

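### An unchanged depression mean is read as a sign of benefit, and the duration explanation offered for it has no support in the questionnaire

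*Combined protocol and SAP*

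**What the plan says.** The design is a "Single-arm study involving five (5) subjects", with one questionnaire before treatment and one after. On the rating scale, "a rating of one (1) on the scale indicates a very severe case of a specific symptom" and "ten (10) indicates that the symptom is not experienced at all", so a higher score is milder.

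The item "Rate The Severity of Depression" has "Average Score: 6.4" at baseline (Prior to the Trial). The After The Trial table shows the same mean and marks it as unchanged.

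The Discussion points out that depression was the only symptom without an average change. It postulates that "this is due to depression being a more deep-rooted issue which was prevalent for an extended period prior to the clinical trial". It next calls it encouraging that depression did not get worse, "indicating that PEMF therapy is able to improve symptoms related to depression (fatigue, insomnia, anger"). It ends by referring the reader to the considerations for future trials.

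The conclusion at the end of Reflections and Considerations says that nearly every symptom studied improved in all patients and that none worsened. It does not name depression.

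**The concern.** Two steps in the Discussion go beyond the data.

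- **From no change to benefit.** A zero on one item is offered as a sign that the treatment helps three other items. The cause of the null is hedged; this inference is not.
- **The duration explanation.** To account for depression staying still while other symptoms moved, it would have to be more entrenched or of longer standing than they were. That needs duration data for depression itself.

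At stake is what a reader takes from the one item that did not move. As written, a zero can be read as support for the treatment. The closing conclusion, which goes on to call the therapy a beneficial alternative to prescription medication, does not correct that reading.

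**Working it through.** **1. Reproduce the reported change.** Change = mean after − mean before, from the tables in Prior to the Trial and After The Trial.

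| Item | Before | After | Change |
|---|---|---|---|
| Depression | 6.4 | 6.4 | 0.0 |
| Fatigue | 5.0 | 6.8 | 1.8 |
| Falling asleep | 5.6 | 8.2 | 2.6 |
| Anger | 4.8 | 7.4 | 2.6 |

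These match the printed changes, as do the other seven items. The dispute is over interpretation, not arithmetic.

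**2. Test the inference.** The premise is that mean depression did not fall. The conclusion is that fatigue, insomnia and anger can be improved. Each of those three is a separate question with its own mean. Any case for them rests on rows two to four of the table, and the depression row adds nothing to it. In the other direction, gains on those rows are not evidence about depression, which was rated directly and did not move. The Study Summary names only a questionnaire with symptom ratings as the endpoint and sets up no depression-related group of items. Earlier in the same Discussion, fatigue is listed among the physical symptoms.

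**3. Look for duration data.** The only duration question is "How long have your symptoms persisted", asked for all symptoms at once. Three patients answered more than three years, one more than a year, and one 8 to 12 months. The same five answers cover the symptoms that improved, so they cannot show that depression lasted longer. The only other closed question that names depression asks about frequency and merges it with anxiety and sensitivity (daily 3, weekly 1, monthly 1). It carries no duration and cannot be separated.

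**4. Baseline rank.** Depression's 6.4 is the highest, so mildest, of the 11 baseline means, which run from 4.6 to 6.4. The next highest is 6.2 (anxiety and happiness). In totals over five patients, 5 × 6.4 = 32 against 5 × 6.2 = 31. The lead is one scale point in one patient.

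**5. What a zero mean shows.** The depression total is 32 before and 32 after, so the five changes sum to zero. Changes of 0, 0, 0, 0, 0 satisfy that, and so do +2, −2, 0, 0, 0 (illustrative values; individual changes are not tabulated). The mean alone cannot tell these apart.

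Precision is also low. No SD of change is reported, so one has to be assumed. The 95% half-width is t(0.975, 4 df) × SD / √5, with t = 2.776:

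- SD 1: 2.776 × 1 / 2.236 = 1.24
- SD 2: 2.776 × 2 / 2.236 = 2.48
- SD 3: 2.776 × 3 / 2.236 = 3.72

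Over that range, a zero observed mean is compatible with an average worsening of about 1.2 to 3.7 points.

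**6. Is the null carried forward?** The bullets under Reflections and Considerations cover study size, spacing of sessions and funding. Depression is not among them, although the Discussion sends the reader there.

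**The case against.** The document is more open than the criticism may suggest. It prints every mean, draws attention to the depression result, offers the cause only as a postulate, and says the lack of change matters for future trials. Its conclusion says nearly all symptoms improved, which signals an exception. The benefit it claims is for related symptoms, not for depression itself. Patient accounts that the Discussion and the Reflections refer to were not in the text available here and might describe depression histories. All of this stands, and it limits the point to one faulty inference and one unsupported explanation.

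Four stronger readings are tempting and should not be adopted.

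- **The baseline scores contradict the deep-rooted explanation.** They do not. The scale measures severity, and a mild symptom can be chronic. The ranking also rests on 0.2 points.
- **The milder items simply changed least, through regression to the mean or lack of room.** Over the eight symptom items, baseline and change correlate at −0.67. Over all 11 items the figure is −0.50; for the eight without depression it is −0.44; without depression and anxiety it is +0.09. Headaches, the most severe item at 4.6, gained only 1.4. Depression had 3.6 points of room; happiness had 3.8 and gained 2.0. Comparing means of different items is in any case no test of regression to the mean. This would replace one post hoc story with another.
- **The null is concealed.** It is reported and flagged.
- **Some patient's depression worsened.** The means do not show that either; they leave it open.

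**Conclusion.** The concern holds in a limited form. Reading a mean change of 0.0 (6.4 to 6.4, n = 5) as an indication of benefit is a non sequitur, whatever the patient accounts contain. The explanation by longer standing is unsupported by the questionnaire, because duration was collected once for all symptoms; it is not shown to be false. That no patient's depression worsened cannot be verified from the tabulated means.

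The finding on the inference needs no assumption. The finding on duration rests on the questionnaire items as reported. The interval widths rest on assumed SDs of 1 to 3 points and serve only to show scale. No estimate in the report changes; what changes is the conclusion drawn from one of its 11 items.

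**What to change.** In the Discussion:

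- Delete the clause that infers an effect on related symptoms from the absence of worsening.
- Delete the duration explanation, or label it untested because no depression-specific duration was collected.
- Add the five individual depression changes. Five responses were collected at each time (Illustrations 1.10 and 2.2). If the forms cannot be linked by patient, say so and give both sets of scores.

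Suggested text:

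> Mean depression score was unchanged (6.4 before and after, n = 5). Individual changes were [five values]. The questionnaire cannot say why, since it recorded duration once for all symptoms together. Changes in fatigue, sleep and anger are reported separately and are not evidence of an effect on depression.

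In the conclusion at the end of Reflections and Considerations, name depression as the item whose mean did not change. Support the statement that no symptom worsened with the individual depression changes, or limit it to means.

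The cost is wording plus one short list of scores already collected. The downside is a less favourable discussion and conclusion.

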## **Reflections and Considerations**

The clinical trial highlights the many benefits of PEMF therapy in treating symptoms related to PTSD and Trauma. All patients felt a significant improvement in their lives and indicated a wish to continue with PEMF therapy after the clinical trial had concluded. It can also be suggested that taking the time out of a daily schedule to attend PEMF therapy allows a patient to relax and rest. This form of meditation can be hypothesised as a beneficial side effect to PEMF therapy.

It should also be noted that patients with previous experience with Cognitive Behavioural Therapy (CBT) were more receptive to treatment, especially within the first two sessions. This is due to the selected patients (two of the five patients in the study) being able to communicate their triggers and emotions more clearly to the Lead Practitioner during PEMF treatment. This allowed the patients to experience a form of CBT with the clinical trial staff, whilst providing them time to relax out of their regular schedule. These two patients especially saw an improvement with sleeping, indicating that the opportunity to vocalise their symptoms and emotions helped them alleviate PTSD-related problems.

Whilst the clinical trial was a success in achieving the primary objective, there are numerous considerations and reflections for further clinical trials into PEMF therapy.

- A larger study would be beneficial in further analysing the benefits of PEMF therapy in treating PTSD and Trauma. Access to a larger cohort of volunteers, with a larger time frame of more PEMF sessions would produce a larger result pool. This would also allow for a control group, a treatment group, and a sham group to compare results more accurately and draw wider conclusions to the specific benefits of PEMF treatment.
- Twice weekly sessions proved to be tiring for patients (see Patient Three's statement above), therefore a longer, more spaced-out study would allow patients to recover from PEMF treatment before their subsequent sessions. This would remove the risk of exhausting the patients which may hamper accurate results of the study.
- This study was restricted due to financial and time restraints. Staff numbers were restricted to the Lead Practitioner and a Research Assistant to disseminate results. The financial impact of conducting a clinical trial for free dictated that the trial would be short to make it viable for the sponsor's funding.

It is of the opinion of the National Centre of Electromagnetic Therapies that this clinical trial was a success in meeting its primary objective in improvement symptoms related to PTSD and Trauma through PEMF. The clinical trial has highlighted the many benefits of PEMF treatment. Nearly all studied symptoms improved for all patients during the trial, and there was no worsening of symptoms recorded. The evidence provided within this document attests to these conclusions.

Therefore, it is recommended that further clinical trials into the development of Pulsed Electromagnetic Therapy as treatment for symptoms of PTSD and Trauma should be conducted. It is our goal to conduct a similar study on a far larger scale, with more participants and a longer trial period. This conclusion has been reached due to the promising positive benefits of PEMF therapy shown through this clinical trial. The clinical trial also concludes that PEMF therapy is a beneficial, non-invasive alternative to prescription medication in relation to PTSD and Trauma. Whilst the results cannot claim to be representative of the entire U.K., the clinical trial has indicated that there are significant benefits to Bio-Resonance treatment and should therefore be studied further.

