## Study Summary

Title	Pulsed ElectroMagnetic Field (PEMF) therapy in Treating Post-Traumatic Stress Disorder (PTSD) & Trauma
Methodology	Single arm observing treatment intervention; no control, no placebo/sham
Study Duration	Estimated duration for the main protocol (the start and end of the treatment programme) is approximately 3 weeks
Study Centre(s)	Private clinic in Bristol, U.K.
Objectives	
Primary Objective: To evaluate the efficacy of Artificial Intelligence (AI) guided software rendering PEMF treatment to treat PTSD & Trauma
 
Secondary Objective: To evaluate the feasibility of AI implementation in drastically reducing the time required to train PEMF therapists, thereby allowing faster adoption of PEMF therapy into mainstream practice through use by other licensed/regulated/trained healthcare professionals such as talking therapists, nurses, doctors, social workers, and carers

Number of Actual Participants	5
Diagnosis and Main Inclusion Criteria	
Inclusion Criteria:
 
 
• Aged 18 or over
 
• Have been diagnosed with PTSD or Trauma
 
• Have been experiencing on-going, continuous symptoms of PTSD or Trauma for at least the past 6 months
 
• Can attend 6 sessions lasting 90 minutes over 3 weeks
 
• Consent and Compliance with all requirements of clinical trial, including dissemination of results, with anonymity of identity provided
 
 
Exclusion Criteria:
 
 
• Under the age of 18 years old
 
• Have not been diagnosed with PTSD or Trauma
 
• Have serious health conditions such as cancer
 
• Unable to attend 6 sessions
 

Study Product, Dose, Route, Regimen	Treatment group will receive 6 sessions, each lasting 1.5 hours of PEMF treatment over the course of 3 weeks through the CE-marked CIO devices

	classified by the U.S. Food & Drug Administration as a Type 11a Medical Device. SCIO devices contain a frequency generator and scanning technology, along with electrode harnesses that connect to the forehead, wrists, and ankles. The devices are controlled by software that is guided by A.I.
Statistical Methodology	Primary Endpoint: Symptoms of PTSD & Trauma are evaluated through a questionnaire, with scale ratings for different symptoms. Symptoms were correlated with information available on the NHS website.

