**Duration of the Study:**

The study is estimated to take place over 3 weeks, with enrolment remaining open until the trial starts. A questionnaire is required to be answered before the first session and after the final session of the clinical trial.

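### A causal conclusion about prior CBT rests on an unplanned comparison of two patients with three, with no scored outcome during treatment and only whole-group averages reported

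*Combined protocol and SAP*

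**What the plan says.** The Study Summary describes the design as "Single arm observing treatment intervention; no control, no placebo/sham", and Study Design gives its size: "Single-arm study involving five (5) subjects undergoing 6 90-minute sessions of Pulsed Electromagnetic Therapy". On assessment, Duration of the Study says: "A questionnaire is required to be answered before the first session and after the final session of the clinical trial". Study Design, the Clinical Trial Outline and After The Trial all agree with that two-point schedule. The only record of anything between the two questionnaires is in During The Trial, where the Lead Practitioner is said to have noted verbal feedback from each patient. No scale or schedule is given for it.

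The second paragraph of Reflections and Considerations then makes three linked statements about patients with earlier Cognitive Behavioural Therapy (CBT), identified as "two of the five patients in the study":

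- They "were more receptive to treatment, especially within the first two sessions".
- A cause follows, opening "This is due to the selected patients": they could explain their triggers and emotions more clearly to the Lead Practitioner. The paragraph adds that this amounted to a kind of CBT with the trial staff.
- "These two patients especially saw an improvement with sleeping", which is read as "indicating that the opportunity to vocalise their symptoms and emotions helped them alleviate PTSD-related problems".

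The results tables in Prior to the Trial and After The Trial give averages over all five patients. They contain no subgroup means, no individual scores and no measure of spread.

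**The concern.** The paragraph reads as a finding with a mechanism attached. The preceding paragraph presents its own suggestion about rest and relaxation as a hypothesis; this one does not.

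Three things are missing beneath it. Prior CBT is not named as a subgroup in the Study Summary or Methods, and the visible text does not define receptiveness. A response confined to the first two of six sessions cannot be seen by a questionnaire given only before the first session and after the last. And two patients against three, with no control, cannot separate CBT history from any other difference between five individuals.

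The attribution of benefit is also at stake. Sleep is one of the two items with the largest average gain in the Discussion (2.6 points), and the closing paragraphs of the document credit the improvement to PEMF. If talking with staff produced part of the sleep gain in two of the five patients, that part cannot be credited to the device alone.

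**Working it through.** **Inputs from the document.** Five patients (Study Design); two with prior CBT, hence three without (Reflections and Considerations); sleep item averages of 5.6 before (Prior to the Trial) and 8.2 after (After The Trial), on a scale from 1 (very severe) to 10 (not experienced).

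**Assumptions not in the document.** A 5% significance level, and the effect size used for power. The document names no test, level or sample-size calculation.

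**1. The document's own figure.** 8.2 - 5.6 = 2.6, as reported. In patient totals, 5 × 5.6 = 28 and 5 × 8.2 = 41, a total gain of 13 points.

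**2. What the average says about the subgroups.** Let c be the total gain of the two CBT patients. The difference in mean change (CBT minus others) is c/2 - (13 - c)/3.

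| Condition | Lowest difference | Highest difference |
|---|---|---|
| No patient worsened | c = 0: 0 - 4.33 = -4.3 | c = 13: 6.5 - 0 = +6.5 |
| Every patient gained at least 1 point | c = 2: 1 - 3.67 = -2.7 | c = 10: 5 - 1 = +4.0 |

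The first condition takes up the closing statement that no worsening was recorded; the second is an added assumption. Both ranges include zero, so the tables do not show even the direction of a subgroup difference.

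**3. The most extreme result possible.** There are C(5,2) = 10 ways to choose two patients from five. If CBT history were irrelevant, these two would still be the top two sleep improvers with probability 1/10. Therefore:

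- the smallest exact one-sided p is 1/10 = 0.10;
- the smallest two-sided Mann-Whitney p is 2/10 = 0.20;
- a two-sided permutation test on the difference in means can reach 1/10 = 0.10, because with unequal groups the opposite split need not be as extreme.

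Hypothetical gains of 4 and 5 against 1, 1 and 2 (total 13, matching the reported average) illustrate the last point. The observed difference is 4.5 - 1.33 = 3.17. The most extreme split the other way gives 1 - 3.67 = -2.67, which is smaller in size, so only one split in 10 is as extreme and p = 0.10. The rank test on the same data gives 0.20.

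**4. A t-test on the same hypothetical gains.** The within-group sums of squares are 0.5 and 0.667, so the pooled variance is 1.167/3 = 0.389. The standard error is √(0.389 × (1/2 + 1/3)) = 0.569, giving t = 3.17/0.569 = 5.56 on 3 degrees of freedom and p of about 0.011. A t-test can therefore cross 5%, but only by relying on normality with groups of two and three. Its power at a true difference of 1 SD (assumed, two-sided 5%) is about 12%. The 95% interval half-width is 3.18 × √(1/2 + 1/3) = about 2.9 SD.

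**5. Choice of item.** Sleep is one of 11 rated items. If the items were independent, the chance that a given pair ranks as the top two on at least one would be 1 - 0.9^11 = 0.69. The items are probably correlated, so this figure is only an illustration.

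**6. Timing.** The sessions run over three weeks and the questionnaires bracket them. No scored value exists at session two, so the first-two-sessions remark can rest only on the verbal feedback.

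**The case against.** The strongest reply is that this is a passing observation. It sits under a heading for reflections, it does not reappear in the Discussion or the closing conclusions, no subgroup analysis was run, and the study is openly small and uncontrolled. That limits the harm, but it does not turn a stated cause into an impression.

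Several stronger readings are tempting and should not be made:

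- *Nothing was observed during treatment.* A reader might infer this from the questionnaire schedule. During The Trial shows that verbal feedback was noted. What is missing is a structured or scored outcome.
- *No result could ever be significant.* This is true of exact tests only. As shown, a t-test could fall below 5%, and the 5% level is itself an assumption.
- *The remark will steer who enters the next study.* The listed considerations cover cohort size, control and sham groups, spacing of sessions and resources. None mentions CBT history.
- *Crediting talking contradicts crediting the device.* The paragraph describes the talking as taking place during PEMF sessions. That is confounding by something delivered alongside the treatment, not a contradiction.

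Parts of the document, apparently including individual patient statements, were not available for this review. They may be the source of the receptiveness and sleep remarks. This is a good reason to relabel the remarks rather than demand that they be struck out. Such notes could not change the 2-versus-3 split or supply a control.

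**Conclusion.** The concern stands as one of unsupported causal interpretation. Both the stated cause and the inference from sleep go beyond what two against three patients in an uncontrolled study can show, and the timing claim has no scored outcome behind it. The published averages leave the subgroup difference in sleep undetermined, from -4.3 to +6.5 points if nobody worsened. The smallest exact p is 0.10 one-sided; two-sided it is 0.20 by rank test, or as low as 0.10 by a permutation test on means, all above the assumed 5% level.

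This does not show that CBT history is irrelevant or that the practitioner's impression is wrong. It shows that the study cannot tell. The whole-group averages are unaffected; what changes is what the document may conclude about these two patients and how far their gains may be credited to PEMF.

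**What to change.** In the second paragraph of Reflections and Considerations:

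- Remove the causal link in the sentence opening "This is due to the selected patients" and the inference "indicating that the opportunity to vocalise their symptoms and emotions helped them alleviate PTSD-related problems".
- Relabel the receptiveness, first-two-sessions and sleep remarks as an unplanned, informal impression of the practitioner in two patients, based on unscored verbal feedback where that is the source, and supporting no conclusion about CBT history.
- State that these patients also talked through their symptoms with staff, that this is a competing explanation, and that their gains therefore cannot be credited to PEMF alone.
- Optionally, list the five individual sleep changes by prior-CBT status. The visible text does not show that the before and after answers are linked by patient, and five rows with therapy history could identify someone. Do this only if linkage exists and the promised anonymity can be kept.

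The required work is rewording one paragraph. The downside for the sponsor is that the document loses an explanatory claim and its attribution of benefit to the device becomes less favourable.
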